Study Site	Medical University of Vienna Department of Clinical Pharmacology [name]

1.5.1

	[name] [contact] [contact] Email: [contact]
Planned Sample Size	Part A: 80 NHVs Part B: 16 NHVs Part C: 8 NHVs Part D: 8 NHVs (including NHVs who may have previously participated in Part A)
Primary Objective	The primary objective of this study is to assess the clinical safety and tolerability of BT200 in NHVs.
Secondary Objectives	The secondary objective of this study is to assess the human PK of BT200.
Exploratory Objectives	The exploratory objectives of this study are to evaluate the human immunogenicity and PD of BT200, as follows: 
 • To evaluate the presence of anti-drug antibodies (ADAs) against BT200 • To evaluate the human pharmacodynamics (PD) of BT200 with respect to VWF-mediated platelet function • To evaluate the human PK/PD relationship of BT200 • To evaluate potentially useful biomarkers for future clinical trials • To investigate the mechanism of action of BT200 on the human coagulation system
Target Population	NHVs
Inclusion Criteria	To be eligible for this study, subjects must meet all of the following inclusion criteria: 
 1. Healthy male or female volunteers, age \geq 18 years old at screening 2. If female, must be post-menopausal or status post hysterectomy 3. Able to comprehend and to give informed consent 4. Able to cooperate with the Investigator, to comply with the requirements of the study, and to complete the full sequence of protocol-related procedures
Exclusion Criteria	Subjects meeting any of the following criteria will be excluded from the study: 
 1. Clinically significant medical history (including von Willebrand Disease, thrombocytopathy, or any type of bleeding diathesis) or ongoing chronic illness that would jeopardize the safety of the subject or compromise the quality of the data derived from his/her participation in this study 2. Clinically relevant abnormal findings on physical examination or clinically relevant laboratory abnormalities 3. History of infusion hypersensitivity reactions, significant drug allergy, or anaphylactic reactions 4. Substance abuse, mental illness, or any reason that makes it unlikely in the judgment of the Investigator for the subject to be able to comply fully with study procedures

1.5.1

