1.3 Endpoints

1.3.1 Primary Endpoint

Overall safety and tolerability of BT200, assessed in terms of:

- Serious, drug-related adverse events (AEs)
- Premature terminations due to drug-related AEs
- Patterns of serious or non-serious, drug-related AEs, and/or clinically relevant laboratory abnormalities, vital signs, ECGs, or physical findings suggestive of one or more specific target organs for toxicity of BT200
- Clinically evident bleeding

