6.4 Other Safety Parameters

Other safety data from scheduled visits will be tabulated as described below. Listings will additionally include results from unscheduled visits or early termination visit.

Results from vital signs (systolic blood pressure [mmHg], diastolic blood pressure [mmHg], heart rate [beats/min], body temperature [C] and body weight [kg]) and ECG will be tabulated descriptively by:

- Absolute values by parameter and time points (summary statistics)
- Absolute changes from randomization by parameter and time points (summary statistics)
- Number of subjects with clinically relevant vital signs results by parameter and time point (frequency statistics)

- ECG Interpretation (normal/abnormal/abnormal, clinically relevant/abnormal, not clinically relevant) by time point (frequency statistics)
- Physical examination results (normal/abnormal) by body system and time point (frequency statistics)

Absolute values of vital signs parameters and continuous ECG parameters will be provided by time point. The x-axis will show the study day. A separate figure will be provided for every parameter.

Details are specified in Section [7](#).

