14.x.3.1.33	Yes	Vital Signs: Absolute change from randomization by time point (Safety Population)	Content see Table 14.x.3.1.32
14.x.3.1.34	Yes	Subjects with clinically relevant vital signs by time point (Safety Population)	Content see Table 14.x.3.1.32
14.x.3.1.35	Yes	ECG: Absolute values by time point (Safety Population)	
 • PQ [ms] • QRS [ms] • QT [ms] • QTcF [ms] • P [ms] • RR [ms] • PP [ms] • P [degree] • QRS [degree] • T [degree]
14.x.3.1.36	Yes	ECG: Absolute change from randomization by time point (Safety Population)	Content see Table 14.x.3.1.35
14.x.3.1.37	Yes	Subjects with clinically relevant ECG values by time point (Safety Population)	Content see Table 14.x.3.1.35
14.x.3.1.38	Yes	ECG Interpretation by time point (Safety Population)	
 • normal • abnormal • abnormal, clinically relevant • abnormal, not clinically relevant
14.x.3.1.39	Yes	Physical Examination results by body system and time point (Safety Population)	
 • normal • abnormal

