			time, same as visit/admission/discharge date, Result, not done, Reason not done, Clinically relevant
16.2.x.3.21	No	Vital Signs	Dose level, Subject number, Visit, Vital signs collection, Reason not collected, Collection date, Collection time, same as visit/admission/discharge date, Test, Result, Clinically relevant, not done
16.2.x.3.22	No	ECG	Dose level, Subject number, Visit, ECG performed, Reason not performed, Date, Time, Same as visit/admission/discharge date, Test, Result, Abnormal, Clinically relevant, not analyzed/not available
16.2.x.3.23	No	Physical Examination	Dose level, Subject number, Visit, Extent of physical examination, Examination performed, Reason not performed, Examination Date, Examination Time, same as visit/admission/discharge date, Body system, Result, Specification other body system

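### Tables of ECG interpretation and physical examination do not link a subject's post-dose result to the pre-dose result, so new findings must be sought by hand in listings that are left out of topline

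*SAP*

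**What the plan says.** SAP section 6.4 plans two categorical safety summaries as frequencies: "Physical examination results (normal/abnormal) by body system and time point (frequency statistics") and "ECG Interpretation (normal/abnormal/abnormal, clinically relevant/abnormal, not clinically relevant) by time point (frequency statistics"). Section 7.1 carries these into Table 14.x.3.1.39, "Physical Examination results by body system and time point (Safety Population"), with rows normal and abnormal, and Table 14.x.3.1.38, "ECG Interpretation by time point (Safety Population"), with rows normal, abnormal, abnormal clinically relevant, and abnormal not clinically relevant. Both tables are marked for topline.

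A within-subject comparison is planned for the measured ECG parameters (Table 14.x.3.1.36, "ECG: Absolute change from randomization by time point (Safety Population")). Table 14.x.3.1.37 counts subjects with clinically relevant ECG values. Section 7.1 contains no table that sets a subject's post-dose category against the pre-dose one.

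In section 7.2, Listings 16.2.x.3.22 (ECG) and 16.2.x.3.23 (physical examination) give results by subject and visit, and both are marked as not in topline. The ECG listing has abnormal and clinically relevant fields. The physical examination listing ends with "Body system, Result, Specification other body system" and has no relevance field.

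The primary endpoint (SAP section 1.3.1) includes ECGs and "physical findings suggestive of one or more specific target organs for toxicity of BT200".

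**The concern.** For a safety endpoint, the question is which findings appeared after dosing. A count of abnormal results at each visit does not answer it when some subjects were already abnormal before dosing: one finding that appears and one that resolves leave the count unchanged.

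Such entry findings are allowed for physical examination. The protocol synopsis excludes only "Clinically relevant abnormal findings on physical examination or clinically relevant laboratory abnormalities", so volunteers with findings judged not relevant can enrol and may be counted as abnormal at later visits.

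Physical examination is the weaker of the two. Its table has no relevance category, and its listing names the body system but has no field for the finding. A long-standing abnormality and a different new one in the same body system would look alike in both outputs. By contrast, the listings for hematology and coagulation, qualitative urinalysis, vital signs and ECG all carry a clinical-relevance field.

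What is at stake is how directly the report, and above all the Part A and Part D topline package, can show new findings by cohort.

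**Working it through.** The plan gives no figure on this point, so there is nothing to reproduce. The check asks what the planned counts can determine.

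**Inputs**
- n = 6 BT200 subjects per Part A cohort column (SAP sections 1.2 and 2.14).
- Pooled Part A placebo: 10 cohorts × 2 = 20 subjects (same sections).
- b = number abnormal before dosing; v = number abnormal at a post-dose visit. Screening and pre-dose visits are scheduled time points, so both counts would appear in the tables.

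**Formula.** With everyone examined at both times, the number newly abnormal lies between max(0, v − b) and min(v, n − b).

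| n | b | v | Lower limit | Upper limit |
|---|---|---|---|---|
| 6 | 0 | 1 | max(0, 1) = 1 | min(1, 6) = 1 |
| 6 | 1 | 1 | max(0, 0) = 0 | min(1, 5) = 1 |
| 6 | 2 | 2 | max(0, 0) = 0 | min(2, 4) = 2 |
| 6 | 3 | 3 | max(0, 0) = 0 | min(3, 3) = 3 |
| 6 | 2 | 3 | max(0, 1) = 1 | min(3, 4) = 3 |
| 20 | 4 | 4 | max(0, 0) = 0 | min(4, 16) = 4 |

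For n = 6 there are 7 × 7 = 49 possible pairs (b, v). The limits coincide whenever b or v is 0 or 6. They differ in the other 5 × 5 = 25 pairs. This counts patterns and is not a probability. If nobody is abnormal before dosing, the planned count is already exact.

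**How often b exceeds 0.** The documents give no rate of harmless findings at entry. As an assumption, let a share p of volunteers have one in a given row of the physical examination table. The chance that a cohort of 6 has at least one is 1 − (1 − p)^6:
- p = 5%: 1 − 0.95^6 = 0.265
- p = 10%: 1 − 0.90^6 = 0.47
- p = 20%: 1 − 0.80^6 = 0.74
- p = 30%: 1 − 0.70^6 = 0.88

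**Which result is the reference.** The SAP measures change from randomization without saying which assessment that is. The schedules in SAP section 1.5 show why this needs stating:
- Parts A, B and D: the examination before dosing on Day 0 is brief, and the full one is at screening. The last pre-dose result may therefore come from different visits for different body systems.
- Part B: the weekly dosing visits have their own examinations at −1 h, which precede a dose but follow earlier ones.
- Part C: randomization and study drug fall on Day −4, with no ECG or physical examination that day. The Day 0, −1 h assessments come about 96 hours after study drug, so screening is the only result before it.

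**The case against.** The strongest case against is that nothing is lost. The two listings show every subject's result at every visit, and they add unscheduled and early termination visits. In cohorts of 8, a reader can compare before and after by eye. This stands for the final report. A reader might infer that new findings cannot be told apart from old ones at all, and the documents do not support that. The limitation applies to the summary tables and to the topline output for Parts A and D (SAP section 2.2), where the tables appear without these listings.

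The ECG side is largely covered. Table 14.x.3.1.38 separates relevant from non-relevant abnormalities, 14.x.3.1.37 counts relevant values and 14.x.3.1.36 gives interval changes. It would be wrong to infer that harmless entry readings hide a clinically relevant ECG change, because they fall in a different row. The exclusion criterion quoted above does not name ECG, so it says nothing about ECG readings at entry.

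It is also tempting to argue that alternating full and brief examinations distorts the counts. That is weak. The table is by body system, SAP section 2.6 reports non-missing numbers and bases percentages on them, and the listing records the extent of the examination.

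Nor can one say that no output describes a finding. The adverse event and medical history listings may do so. Whether every new abnormality must be recorded there cannot be settled from the protocol text reviewed, which is the synopsis and study diagram.

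Finally, the study is descriptive and no decision rule rests on these counts. That limits the severity but does not remove the gap.

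**Conclusion.** The point holds in a limited form. Tables 14.x.3.1.38 and 14.x.3.1.39 are unlinked counts by visit. Once at least one subject, but not all, is abnormal at both times, they do not fix the number newly abnormal. With 2 of 6 before and 2 of 6 after, that number may be 0, 1 or 2.

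This range follows from the table layout and needs no assumed rate. How often it matters depends on how common harmless entry findings are, which the documents do not say; if there are none, the problem disappears. The gap is greatest for physical examination, which lacks a relevance field in both table and listing, and modest for ECG.

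This is a minor reporting improvement to a component of the primary endpoint. A reader might infer that the safety conclusions are unsound, but the subject-level listings in the final report mean that the documents do not support that.

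**What to change.** 1. In SAP section 6.4 and Tables 14.x.3.1.38 and 14.x.3.1.39, add a shift tabulation of each post-dose result, and of the worst one, against the pre-dose reference. For physical examination, do this per body system. Show the number of newly abnormal subjects descriptively, not as a new numeric endpoint, over subjects with both results.
2. Define the reference as the last result before the first dose of BT200 or placebo in that study part:
   - screening for any body system that the brief pre-dose examination did not cover;
   - screening in Part C;
   - in Part B, the result before the Day 0 loading dose, not the later weekly −1 h visits.
3. Make the ECG interpretation categories mutually exclusive, or label the plain abnormal row as a subtotal of the two below it.
4. In Listing 16.2.x.3.23, add a flag for findings new since the pre-dose reference. Add the finding and its clinical relevance if the eCRF records them.

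The shift tabulations and the flag use results that are already scheduled for collection. The cost is SAP wording, some programming and slightly larger tables. Whether the description and relevance fields in step 4 can be added depends on the eCRF.

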7.2 List of Data Listings

No	Topline Analysis	Title	Content/Comment
Overall Study Information and Baseline Evaluation			
16.2.x.1.1	No	Analysis Population Details	Actual dose cohort, Randomized dose cohort, Subject number, Sentinel (only applicable for Part A), Randomization performed, Date of randomization, Time of randomization, Reason not randomized, Safety Population, Reason not in Safety Population, PP Population, Reason not in PP Population
16.2.x.1.2	No	Screening Failures with Reasons	Subject number, Informed consent date, Subject's withdrawal of consent, In/Ex criterion fulfilled, Adverse event, Other, Specification other reason
16.2.x.1.3	No	Violated Entry Criteria	Subject number, Visit, Criterion ID not met, Criterion description
16.2.x.1.4	No	Visit Information and Admission/Discharge Inpatient Unit	Dose cohort, Subject number, Visit, Reason for unscheduled visit, Visit/Admission/Discharge date, Visit/Admission/Discharge time, Reason visit not performed, Reason outside time window, Specification other reason, Age
16.2.x.1.5	No	Missed Visits due to Covid-19	Dose cohort, Subject number, Visit, Reason for unscheduled visit, Visit date, Visit time, Reason visit not performed, Reason outside time window, Age
16.2.x.1.6	No	Protocol Deviations	Dose cohort, Subject number, PD category, Classification, Reason for classification, PD description
16.2.x.1.7	Yes	Study End Information	Dose cohort, Subject number, Visit attendance status, Date of discontinuation, Primary reason for early termination, Specification other reason, Reason for recommended withdrawal, Death date, Primary cause of death
16.2.x.1.8	Yes	Drop-outs due to Covid-19	Dose cohort, Subject number, Visit attendance status, Date of discontinuation, Primary reason for early termination, Specification other reason, Reason for recommended withdrawal, Death date, Primary cause of death
16.2.x.1.9	Yes	Demographic Data	Dose cohort, Subject number, Subject re-screened (only applicable for Part D), Subject number in Part A (only applicable for Part D), Date of informed consent, Year of birth, Age [years], Gender, Childbearing potential, Reason no childbearing potential, Specification other reason childbearing potential, Race, Specification other race, Ethnicity, Blood type, Rhesus factor, Body weight [kg] at

			screening, Body Height [cm], BMI [kg/m ²] at screening
16.2.x.1.10	No	Medical History	Dose cohort, Subject number, Condition, SOC, PT, Start date, End date, Ongoing at study end
16.2.x.1.11	No	Concomitant Medications	Dose cohort, Subject number, Medication/Therapy, ATC Level 2, ATC Level 3, Start date, End date, Ongoing at study end, Dose, Dose Unit, Dose Form, Frequency, Route, Indication category, prior/concomitant
16.2.x.1.12	No	Concomitant Procedures	Dose cohort, Subject number, Procedure, SOC, PT, Start date, End date, Ongoing at study end, Indication category, Indication, prior/concomitant
16.2.x.1.13	No	Serology	Dose cohort, Subject number, Visit, Serology sample collected, Reason not collected, Collection date, Collection time, Test name, Result, Not done
16.2.x.1.14	No	Screening for coronavirus by nasal swab testing (only applicable for Part B and C)	Dose cohort, Subject number, Sample collected, Reason not collected, Collection date, Collection time, Result
Pharmacodynamics/Biomarker/Immunogenicity			
16.2.x.2.1	Yes	Pharmacodynamics Results	Dose cohort, Subject number, Visit, Sampling Date/Time, Sample taken, Reason not done, Test, Result specification, Result, Unit, Absolute Change, Relative Change [%]
16.2.x.2.2	Yes	Biomarker Results	Dose cohort, Subject number, Visit, Sampling Date/Time, Sample taken, Reason not done, Test, Result specification, Result, Unit, Absolute Change, Relative Change [%]
16.2.x.2.2	Yes	Additional Biomarker Results	Dose cohort, Subject number, Visit, Parameter, Result, Unit, Absolute Change, Relative Change [%]
16.2.x.2.3	No	ADA Results	Dose cohort, Subject number, Nominal Day, Collection date, Collection time, Ave, Stdev, CV%, Reported Result
Safety Analysis			
16.2.x.3.1.1	Yes	Study Drug Administration	Dose cohort, Subject number, Visit, Study drug administered, Study drug administered as, Reason not administered, Administration Start Date, Administration Start Time, Administration End Date, Administration End Time, Location, Other Location, Dose level, Study drug administration performed according to protocol, Cumulative dose level (only applicable for Part B)
16.2.x.3.1.2	Yes	Desmopressin Administration (only applicable for Part C)	Dose cohort, Subject number, Desmopressin administered, Reason not administered, Administration Start Date, Administration Start Time, Administration End Date, Administration End Time, Administration dose (ug)

16.2.x.3.2	Yes	Adverse Events (Part I)	Dose cohort, Subject number, Source, Term, SOC, PT, Start date, Start time, Serious, Serious Criteria, Severity, Causality to study treatment, Causality to desmopressin (only applicable for Part C)
16.2.x.3.3	Yes	Adverse Events (Part II)	Dose cohort, Subject number, AE Term, Action taken on study treatment, Action taken on desmopressin (only applicable for Part C), Other action taken, Specification other action taken, Outcome, Recovering date, recovering time, Ongoing at final examination
16.2.x.3.4	Yes	Serious Adverse Events (Part I)	See Listing 16.x.3.1
16.2.x.3.5	Yes	Serious Adverse Events (Part II)	See Listing 16.x.3.2
16.2.x.3.6	Yes	Haemorrhage terms (SMQ) (Part I)	See Listing 16.x.3.1
16.2.x.3.7	Yes	Haemorrhage terms (SMQ) (Part II)	See Listing 16.x.3.2
16.2.x.3.8	Yes	Embolic and thrombotic events, arterial (SMQ) (Part I)	See Listing 16.x.3.1
16.2.x.3.9	Yes	Embolic and thrombotic events, arterial (SMQ) (Part II)	See Listing 16.x.3.2
16.2.x.3.10	Yes	Embolic and thrombotic events, vessel type unspecified and mixed arterial and venous (SMQ) (Part I)	See Listing 16.x.3.1
16.2.x.3.11	Yes	Embolic and thrombotic events, vessel type unspecified and mixed arterial and venous (SMQ) (Part II)	See Listing 16.x.3.2
16.2.x.3.12	Yes	Embolic and thrombotic events, venous (SMQ) (Part I)	See Listing 16.x.3.1
16.2.x.3.13	Yes	Embolic and thrombotic events, venous (SMQ) (Part II)	See Listing 16.x.3.2
16.2.x.3.14	No	Adverse Events with missing assessments (Part I)	See Listing 16.x.3.1
16.2.x.3.15	No	Adverse Events with missing assessments (Part II)	See Listing 16.x.3.2
16.2.x.3.16	Yes	Additional Assessments for Bleeding Events	Dose cohort, Subject number, Bleeding event, Bleeding event verbatim, Start date, Start time, Bleeding Assessment Score, ISTH clinical relevant major bleeding, Major bleeding criteria, ISTH clinical relevant non-major bleeding, Non-major bleeding criteria, End date, End time
16.2.x.3.17	Yes	Hematology and Coagulation Values Outside Normal Range	Dose Level, Subject number, Parameter, Visit, Lab performed, Reason not performed, Collection date, Collection time, same as visit/admission/discharge date, Test, Result, Unit, not done, Reason not done, Outside laboratory limits, Lower limit, Upper limit, Clinically relevant
16.2.x.3.18	Yes	Clinical Chemistry Values Outside Normal Range	See Listing 16.x.3.9
16.2.x.3.19	No	Quantitative Urinalysis Values Outside Normal Range	See Listing 16.x.3.9
16.2.x.3.20	No	Abnormal Qualitative Urinalysis Results	Dose level, Subject number, Parameter, Visit, Lab performed, Reason not performed, Collection date, Collection

			time, same as visit/admission/discharge date, Result, not done, Reason not done, Clinically relevant
16.2.x.3.21	No	Vital Signs	Dose level, Subject number, Visit, Vital signs collection, Reason not collected, Collection date, Collection time, same as visit/admission/discharge date, Test, Result, Clinically relevant, not done
16.2.x.3.22	No	ECG	Dose level, Subject number, Visit, ECG performed, Reason not performed, Date, Time, Same as visit/admission/discharge date, Test, Result, Abnormal, Clinically relevant, not analyzed/not available
16.2.x.3.23	No	Physical Examination	Dose level, Subject number, Visit, Extent of physical examination, Examination performed, Reason not performed, Examination Date, Examination Time, same as visit/admission/discharge date, Body system, Result, Specification other body system

7.3 List of Figures

No	Topline Analysis	Title	Content/Comment
PD / Biomarker			
14.x.2.1.29	Yes	Multiplate Aggregometer [U]: Absolute values by subject (PP Population)	
14.x.2.1.30	Yes	Multiplate Aggregometer [U]: Absolute values by cohort (PP Population)	
14.x.2.1.31	Yes	PFA-100 [sec]: Absolute values by subject (PP Population)	
14.x.2.1.32	Yes	PFA-100 [sec]: Absolute values by cohort (PP Population)	
14.x.2.1.33	Yes	REAADS: Absolute values by subject (PP Population)	
14.x.2.1.34	Yes	REAADS: Absolute values by cohort (PP Population)	
14.x.2.1.35	Yes	VWF:RiCo [%]: Absolute values by subject (PP Population)	
14.x.2.1.36	Yes	VWF:RiCo [%]: Absolute values by cohort (PP Population)	
14.x.2.1.37	Yes	VWF antigen [%]: Absolute values by subject (PP Population)	
14.x.2.1.38	Yes	VWF antigen [%]: Absolute values by cohort (PP Population)	
14.x.2.1.39	Yes	VWF propeptide [mIU/mL]: Absolute values by subject (PP Population)	
14.x.2.1.40	Yes	VWF propeptide [mIU/mL]: Absolute values by cohort (PP Population)	
14.x.2.1.41	Yes	Factor VIIIic activity [%]: Absolute values by subject (PP Population)	
14.x.2.1.42	Yes	Factor VIIIic activity [%]: Absolute values by cohort (PP Population)	
14.x.2.1.43	Yes	APTT FS [sec]: Absolute values by subject (PP Population)	

14.x.2.1.44	Yes	aPTT FS [sec]: Absolute values by cohort (PP Population)	
14.x.2.1.45	Yes	Thrombinoscope [nM]: Absolute values by subject (PP Population)	
14.x.2.1.46	Yes	Thrombinoscope [nM]: Absolute values by cohort (PP Population)	
14.x.2.1.47	Yes	Fibrin D-dimer [mIU/mL]: Absolute values by subject (PP Population)	
14.x.2.1.48	Yes	Fibrin D-dimer [mIU/mL]: Absolute values by cohort (PP Population)	
14.x.2.1.49	Yes	Prothrombin fragment F1.2 [mIU/mL]: Absolute values by subject (PP Population)	
14.x.2.1.50	Yes	Prothrombin fragment F1.2 [mIU/mL]: Absolute values by cohort (PP Population)	
Safety Analysis			
14.x.3.1.40	Yes	Boxplots of hematology values by group and visit (Safety Population)	Separate figures for every group and every parameter
14.x.3.1.41	Yes	Boxplots of coagulation values by group and visit (Safety Population)	Separate figures for every group and every parameter
14.x.3.1.42	Yes	Boxplots of clinical chemistry values by group and visit (Safety Population)	Separate figures for every group and every parameter
14.x.3.1.43	Yes	Boxplots of urinalysis values by group and visit (Safety Population)	Separate figures for every group and every parameter
14.x.3.1.44	Yes	Vital signs values by group and visit (Safety Population)	Separate figures for every group and every parameter
14.x.3.1.45	Yes	ECG values by group and Visit (Safety Population)	Separate figures for every group and every parameter

